### 6.1 Observations by Visit

#### 6.1.1 Screening Visit – All Patients

The following assessments will be performed during the Screening Visit, which should take place within 30 days before the first administration of IMP:

ission

- Obtaining voluntarily given, written (signed and dated) informed consent
- Check of inclusion and exclusion criteria
- Demographics: age, ethnic origin
- Blood type (ABO) •
- CD4+ count
- Medical history ٠
- Details on medications taken within one month before screening, including FVIII it written dosing in the previous 6 months, and any concomitant medications.
- Body weight •
- Height ٠
- Physical examination
- Hemophilia Joint Health Score (HJHS)
- Target joint(s) (defined as three or more spontaneous bleeding episodes into a single joint within 6 consecutive months preceding screening visit)
- Vital signs: systolic and diastolic blood pressure, body temperature, pulse (before blood sample collection)
- Blood sample for FVIII inhibitor measurement (modified Nijmegen Bethesda assay)
- Routine safety lab: Hematology: red blood cell count, white blood cell count, ٠ hemoglobin, hematocrit, platelet count; Clinical chemistry: total bilirubin, ALT, AST, urea, serum creatinine, lactate dehydrogenase
- Start of monitoring of adverse events (AEs)
- Cohort 6: LumiTope assay (negative test result required)

Any bleeding episodes occurring between the Screening Visit and the first exposure to OCTA101 or Nuwig should be treated with the patient's previously used FVIII concentrate.

Following screening, eligible patients will receive a patient diary after the first injection of OCTA101 or Nuwiq. The investigator will explain to the patient how to fill in the diary and will emphasize the importance of carefully documenting all treatment details, adverse events, and concomitant medications.

PK assessments are to be performed after a washout period of at least 72 h, if possible, from the last FVIII injection. Patients must not be experiencing any bleeding.

# 6.1.2 Cohort 1 patients – single dose PK, OCTA101 50 IU/kg sc

The following assessments will be performed:

Body weight (before injection)

Property

- Vital signs (before injection, 0.5 h, 8 h, 24 h, 48 h and 72 h after injection)
- Routine safety lab (before injection, 0.5 h, 8 h, 24 h, 48 h and 72 h after injection)
- Blood sample for FVIII inhibitor measurement (modified Nijmegen Bethesda assay), (before injection)
- Blood sample for anti-OCTA12 measurement (before injection)

- Blood samples for measurement of FVIII:C (one-stage and chromogenic assay) (before injection and 0.5 h, 2 h, 4 h, 8 h, 24 h, 48 h and 72 h after injection).
- Blood samples for measurement of OCTA12, as above for FVIII:C •
- tten permission Assessment of local injection site reactions (directly after injection and  $15 \pm 5$  min post-• injection)
- Adverse event monitoring throughout the study period ٠
- Documentation of concomitant medication throughout the study period

#### 6.1.3 Cohort 2 patients – single dose PK, OCTA101 100 IU/kg sc

The following assessments will be performed:

- Body weight (before injection)
- Vital signs (before injection, 0.5 h, 8 h, 24 h, 48 h, 72 h and 96 h after injection) •
- Routine safety lab (before injection, 0.5 h, 8 h, 24 h, 48 h, 72 h and 96 h after injection)
- Blood sample for FVIII inhibitor measurement (modified Nijmegen Bethesda assay), • (before injection)
- Blood sample for anti-OCTA12 measurement (before injection) •
- Blood samples for measurement of FVIII:C (one-stage and chromogenic assay) (before injection and 0.5 h, 2 h, 4 h, 8 h, 24 h, 48 h, 72 h and 96 h after injection).
- Blood samples for measurement of OCTA12, as above for FVIII:C
- Assessment of local injection site reactions (directly after injection and  $15 \pm 5$  min post-• injection)
- Adverse event monitoring throughout the study period •
- Documentation of concomitant medication throughout the study period •

#### 6.1.4 Cohort 3 patients – single dose PK, PK Nuwiq 50 IU/kg iv, followed by OCTA101 50 IU/kg sc into the abdomen

NUWIQ injection (iv): the following assessments will be performed:

Body weight (before injection) •

Property

- Vital signs (before injection, 0.5 h, 8 h, 24 h, 48 h, and 72 h after injection)
- Routine safety lab (before injection, 0.5 h, 8 h, 24 h, 48 h, and 72 h after injection)
- Blood sample for FVIII inhibitor measurement (modified Nijmegen Bethesda assay), (before injection)
- Blood samples for measurement of FVIII:C (one-stage and chromogenic assay) (before injection and 0.5 h, 2 h, 4 h, 8 h, 24 h, 48 h, and 72 h after injection.
- Adverse event monitoring throughout the study period
- Documentation of concomitant medication throughout the study period

OCTA101 injection (sc into the abdomen): the following assessments will be performed:

- Blood sample for anti-OCTA12 measurement (before injection)
- Vital signs (before injection, 8 h, 12 h, 24 h, 48 h, and 72 h after injection)
- Routine safety lab (before injection, 8 h, 12 h, 24 h, 48 h, and 72 h after injection)

- Blood samples for measurement of FVIII:C (one-stage and chromogenic assay) (before injection and 2 h, 4 h, 8 h, 12 h, 24 h, 48 h, and 72 h after injection).
- Blood samples for measurement of OCTA12, as above for FVIII:C •
- permission Assessment of local injection site reactions (directly after injection and  $15 \pm 5$  min post-• injection)
- Adverse event monitoring throughout the study period ٠
- Documentation of concomitant medication throughout the study period

### 6.1.5 Cohort 4 patients – single dose PK, OCTA101 50 IU/kg sc into the thigh

Cancelled.

#### Cohort 5 patients – single dose PK of OCTA101 20 IU/kg sc, followed by single 6.1.6 dose PK of OCTA101 40 IU/kg sc, followed by single dose PK of OCTA101 60 IU/kg sc

OCTA101 injection 20 IU/kg into the abdomen (4 patients): the following assessments will be performed:

- Body weight (before injection)
- Vital signs (before injection, 8 h, 12 h, 24 h, 48 h and 72 h after the injection)
- Routine safety lab (before injection, 8 h, 12 h, 24 h, 48 h and 72 h after the injection) ٠
- Blood sample for FVIII inhibitor measurement (modified Nijmegen Bethesda assay), • (before the first injection)
- Blood sample for anti-OCTA12 measurement (before the injection) •
- Blood samples for measurement of FVIII:C (one-stage and chromogenic assay) (before • the injection and 2 h, 4 h, 8 h, 12 h, 24 h, 48 h, and 72 h after the injection)
- Blood samples for measurement of OCTA12, as above for FVIII:C •
- Assessment of local injection site reactions (directly after injection and  $15 \pm 5$  min post-• injection)
- Adverse event monitoring throughout the study period
- Documentation of concomitant medication throughout the study period

OCTA101 injection 40 IU/kg into the abdomen (4 patients): the following assessments will be performed:

- Vital signs (before injection, 8 h, 12 h, 24 h, 48 h, and 72 h after the injection)
- Routine safety lab (before injection, 8 h, 12 h, 24 h, 48 h, and 72 h after the injection)
- Blood samples for measurement of FVIII:C (one-stage and chromogenic assay) (before the injection and 2 h, 4 h, 8 h, 12 h, 24 h, 48 h, and 72 h after the injection)
- Blood samples for measurement of OCTA12, as above for FVIII:C
- Assessment of local injection site reactions (directly after injection and  $15 \pm 5$  min postinjection)
- Adverse event monitoring throughout the study period
- Documentation of concomitant medication throughout the study period

OCTA101 injection 60 IU/kg into the abdomen (4 patients): the following assessments will be performed:

- Vital signs (before injection, 8 h, 12 h, 24 h, 48 h, and 72 h after the injection)
- Routine safety lab (before injection, 8 h, 12 h, 24 h, 48 h, and 72 h after the injection)
- Blood sample for FVIII inhibitor measurement (modified Nijmegen Bethesda assay)
   4 weeks after injection
- Blood sample for anti-OCTA12 measurement 4 weeks after injection
- Blood samples for measurement of FVIII:C (one-stage and chromogenic assay) (before the injection and 2 h, 4 h, 8 h, 12 h, 24 h, 48 h, and 72 h after the injection)
- Blood samples for measurement of OCTA12, as above for FVIII:C
- Assessment of local injection site reactions (directly after injection and 15 ± 5 min postinjection)
- Adverse event monitoring throughout the study period
- Documentation of concomitant medication throughout the study period

# 6.1.7 Cohort 1, 2 and 3 patients – daily injections for 3 months, OCTA101 40 - 60 IU/kg sc

Patients entering the 3-month daily prophylactic part will be trained in sc self-administration of study medication. Patients in Cohort 1 will be required to return to the study site for their first daily dose; patients in Cohorts 2 and 3 will still be present at the study site at the time of their first daily dose. The following assessments will be performed:

- Vital signs (before and 3 h and 6 h after the injection at the beginning of the 3-month daily dosing and 0.5, 1, 2, and 3 months thereafter)
- Routine safety lab (before and 3 h and 6 h after the injection at the beginning and 2, 4, 8 and 12 weeks thereafter)
- Blood sample for FVIII inhibitor measurement (modified Nijmegen Bethesda assay), (before the first injection and 0.5, 1, 2 and 3 months thereafter)
- Blood sample for anti-OCTA12 measurement, (before the first injection and 0.5, 1, 2 and 3 months thereafter)
- Blood sample for FVIII:C measurement (one-stage and chromogenic assay), (before and 3 h and 6 h after the injection at the beginning and 0.5, 1, 2, and 3 months thereafter)
- Blood sample for OCTA12 measurement, (before and 3 h and 6 h after injection at the beginning and 0.5, 1, 2, and 3 months thereafter)
- Assessment of local injection site reactions (directly after injection and  $15 \pm 5$  min postinjection, for each injection)
- Physical examination (at End of Study) (Cohort 3 only)
- Adverse event monitoring throughout the study period

Property

• Documentation of concomitant medication throughout the study period

### 6.1.8 Cohort 1 and 2 patients – PK assessment following 3-month daily prophylaxis

Patients from Cohorts 1 and 2 completing the 3-month daily prophylactic part will attend the study site. The following assessments will be performed:

- After a wash-out of at least 72 hours after the last OCTA101 injection, or any other FVIII injection, a dose of 50 IU/kg OCTA101 sc will be administered
- Blood sample for FVIII inhibitor measurement (modified Nijmegen Bethesda assay), (before and at 21 days after the injection)
- Blood sample for anti-OCTA12 measurement, (before and at 21 days after the injection)
- Blood sample for FVIII:C measurement (one-stage and chromogenic assay), (before and 2 h, 4 h, 8 h, 12 h, 24 h, 48 h, 72 h, 96 h, and 120 h after the injection)
- Blood sample for OCTA12 measurement, (before and 2 h, 4 h, 8 h, 24 h, 48 h, 72 h, 96 h, 120 h, 7 days, 14 days, and 21 days after the injection)
- Physical examination (at End of Study)
- Assessment of local injection site reactions (directly after injection and 15 ± 5 min postinjection)
- Adverse event monitoring throughout the study period
- Documentation of concomitant medication throughout the study period
- 6.1.9 Cohort 6: Following a 4-6 week prophylactic treatment phase with ~30 IU/kg Nuwiq iv 3 x weekly, patients start 6-7 months daily treatment with 12.5 IU/kg OCTA101 sc, then 6-7 months daily 25 IU/kg OCTA101 sc (and probably 40 IU/kg OCTA101 sc, depending on the results of earlier treatment phases)

Patients in Cohort 6 will have their first Nuwiq administered at the study site. After the run-in period, patients will be trained in sc OCTA101 self-administration for subsequent home treatment.

The following assessments will be performed:

Start of 4 to 6 week Nuwiq run-in:

- Documentation of bleeding episodes and their treatment throughout the run-in period
- Adverse event monitoring throughout the run-in period
- Documentation of concomitant medication throughout the run-in period

Daily OCTA101 treatment periods:

- Vital signs (before and 8 h after the injection OCTA101 at the beginning of each dosing period and 0.5, 1, 2, 3, 4, 5 and 6 months thereafter)
- Routine safety lab (before and 8 h after the OCTA101 injection at the beginning of each dosing period and 0.5, 1, 2, 3, 4, 5 and 6 months thereafter)
- Blood sample for FVIII inhibitor measurement (modified Nijmegen Bethesda assay), (before the first injection of OCTA101 and 0.5, 1, 2, 3, 4, 5 and 6 months thereafter for each of the 6-7 month OCTA101 daily prophylaxis treatment periods)
- Blood sample for anti-OCTA12 measurement, (before the first injection of OCTA101 and 0.5, 1, 2, 3, 4, 5 and 6 months thereafter for each of the 6-7 month OCTA101 daily prophylaxis treatment periods)
- Blood sample for FVIII:C measurement (one-stage and chromogenic assay), (before and 8°h after the OCTA101 injection at the beginning of the 6-7 months dosing periods and 0.5, 1, 2, 3, 4, 5 and 6 months thereafter)

- Blood sample for OCTA12 measurement, (before the first injection of OCTA101 and 0.5, 1, 2, 3, 4, 5 and 6 months thereafter for each dosing period)
- Physical examination (at End of Study)
- LumiTope assay (before the first injection of OCTA101 and 0.5, 1, 2, 3, 4, 5 and 6 months thereafter for each dosing period)
- Assessment of local injection site reactions (directly after injection and 15 ± 5 min postinjection, for each injection)
- Documentation of bleeding episodes and their treatment throughout the study period
- Adverse event monitoring throughout the study period
- Documentation of concomitant medication throughout the study period

#### 6.1.10 Unscheduled visits

In case of positive inhibitor results, inhibitor retesting using a second, separately drawn sample should be performed, preferably within 15 days of becoming aware of the positive result. Other reasons for unscheduled visits may be the occurrence of serious AEs or hospitalizations due to severe bleeding episodes.

#### 6.1.11 Final visits

All patients will immediately stop treatment with OCTA101, if another patient develops a confirmed FVIII inhibitor ( $\geq 0.6$  BU).

In this case, all FVIII inhibitor negative patients will switch to prophylactic treatment with Nuwiq comparable to the run-in phase, and will come for a final follow-up visit after treatment change. During the final follow-up visit the following should be done:

- Routine safety lab
- Blood sample for FVIII inhibitor measurement (modified Nijmegen Bethesda assay)
- Blood sample for anti-OCTA12 measurement
- Blood sample for OCTA12 measurement
- Physical examination
- LumiTope assay
- Documentation of bleeding episodes and their treatment
- Adverse event monitoring
- Documentation of concomitant medication

### 6.1.12 Time Windows Used in this Study, including Tolerances

In this study, the following time windows and tolerances apply:

Time point	Time stated	Tolerance
Interval between visits	x-month daily prophylaxis part: at 0.5, 1, 2, 3, 4, 5 and 6 months	± 4 days
Blood sampling	before IMP administration	≤ 30 minutes
	30 minutes after IMP administration	± 10 minutes
	1–6 hours after IMP administration	± 15 minutes
	7–12 hours	± 1 hour
	13–24 hours	± 2 hours
	> 24-120 hours	± 3 hours
	7 days	±1 day
	14 days	± 2 days
	21 days	± 3 days
Inhibitor testing	4 weeks	± 1 week 🗙 💙

Table 2:Time Windows Used in this Study

#### 6.2 Duration of Study

#### 6.2.1 Planned Duration for an Individual Patient

The duration of the entire study for an individual patient according to protocol will range from 5 days (patients from Cohort 5) until up to approximately 10 months (patients from Cohort 6), not counting the time period between the screening visit and the first administration of IMP, or patients undergoing immune tolerance induction therapy.

### 6.2.2 Planned Duration for the Study as a Whole

The study will be considered completed when all patients have completed the planned observation period.

The start of the study (enrolment of first patient) was Q2 2019, and the estimated end of the study (last visit of last patient) is Q3 2022.

### 6.2.3 Premature Termination of the Study

Both the Investigator and the Sponsor reserve the right to terminate the study at any time. In this event, any necessary procedures will be arranged on an individual study basis after review and consultation by both parties. In terminating the study, the Sponsor and the Investigator will ensure that adequate consideration is given to the protection of the patients' interests.

Regulatory authorities and IECs/IRBs should be informed in accordance with national regulations.

Early termination of the study as a whole or by center may apply for the following reasons:

### 6.2.3.1 Early Termination of the Entire Clinical Study

At any time, the study as a whole will be terminated prematurely if:

• New toxicological or pharmacological findings or safety reports invalidate the earlier positive benefit-risk-assessment.

Study Protocol No. SubQ8-01, Version 9.0 CONFIDENTIAL

- A single death event (with the exception of death from underlying disease or any other death clearly unrelated to OCTA101) that occurs within 30 days of administration of study drug.
- If clinical development of OCTA101 is terminated for any reason.

According to the revised stopping rules implemented by Amendment 2, the study was to be put on hold until a further DMC recommendation for further conduct of the study was made, if more than one patient met the following criteria:

• Exhibits a consistently high titer inhibitor (≥5 BU), as determined by central laboratory tests including a retest as detailed in Section 0.

or

• Exhibits a low titer inhibitor (≥0.6 BU and <5 BU), as determined by central laboratory test, including a retest as detailed in Section 0, and a standard recovery test using intravenous factor VIII shows a recovery below 66%. A formal half-life study with determination of the terminal half-life (t½) associated with the recovery study is encouraged with the patient in a non-bleeding state and free of any intercurrent illness.

As a further patient with inhibitors in Cohort 2 subsequently met these criteria, the study was put on hold and patients stopped OCTA101 treatment. The ongoing patients in Cohort 3 were switched to Nuwiq prophylaxis for the remainder of the planned 3-month prophylaxis period.

The study will be terminated if another patient develops an inhibitor ( $\geq 0.6$  BU).

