# 7.3.2.2 Collection of AEs

The condition of the patient will be monitored throughout the study. At each visit, whether scheduled or unscheduled, AEs will be elicited using a standard nonleading question such as "How have you been since the last visit/during the previous study period?" In addition, the Investigator will check the patient diaries (if applicable) for any documented event.

Any AE or ADR which occurs during the study will be noted in detail on the appropriate pages of the eCRF. If the patient reports several signs or symptoms representing a single syndrome or diagnosis, the diagnosis should be recorded in the eCRF. The Investigator will grade the severity of all AEs or ADRs (mild, moderate, or severe), the seriousness (non-serious or serious), and the causality as defined in Sections 7.3.2.3, 7.3.3, and 7.3.2.4. The Sponsor is responsible for assessing the expectedness of each ADR (expected or unexpected) as defined in Section 7.3.2.5.

In the event of clinically significant abnormal laboratory findings, the tests will be confirmed, and the patient followed up until the laboratory values have returned to normal and/or an adequate explanation for the abnormality has become available.

Diseases, signs and symptoms, and/or laboratory abnormalities already present before the first administration of IMP will not be considered AEs unless an exacerbation in intensity or frequency (worsening) occurs.

The Investigator will provide detailed information about any abnormalities and about the nature of and reasons for any action taken as well as any other observations or comments that may be useful for the interpretation and understanding of an AE or ADR.

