#### 7.3.2.6 Outcome of AEs

The outcome of all reported AEs has to be documented as follows:

- 1. Recovered, resolved
- 2. Recovering, resolving
- 3. Not recovered, not resolved
- 4. Recovered, resolved with sequelae
- 5. Fatal
- 6. Unknown

NOTE: A patient's death per se is not an event, but an outcome. The event which resulted in the patient's death must be fully documented and reported, even in case the death occurs within 4 weeks after IMP treatment end and regardless of whether or not it is considered treatmentrelated.

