#### 7.3.4 SAE Reporting Timelines

All SAEs, whether or not they are suspected to be related to study treatment, are to be reported immediately by telephone, fax, or email to the Clinical Project Manager or designee:

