#### 7.3.7 Other Relevant Safety Information

#### a) Post-study related safety reports

Any SAE which occurs up to 4 weeks after the last IMP administration should be reported by the Investigator to the Sponsor in case the Investigator becomes aware of it. Proactive monitoring for post-study SAEs is not required.

In case a post-study SAE is identified, the Investigator should complete an SAE form and also state the relation to the clinical study in the report.

Deaths occurring within 4 weeks after the last IMP administration should also be reported, regardless of whether or not they are considered treatment-related.

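### For patients who have finished or left the study, the death reporting window (4 weeks after last IMP) does not match the death stopping rule (30 days after study drug), and Cohort 6 has no timed contact to cover it

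*Protocol*

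**What the plan says.** **Stopping rule.** Protocol Section 6.2.3.1 and the Stopping rules in the Study Outline make a single death "that occurs within 30 days of administration of study drug" a reason to terminate the study. Deaths from underlying disease, and deaths clearly not caused by OCTA101, are excepted.

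**Post-study reporting.** Section 7.3.7 a) says: "Any SAE which occurs up to 4 weeks after the last IMP administration should be reported by the Investigator to the Sponsor", with the condition "in case the Investigator becomes aware of it". It then says: "Proactive monitoring for post-study SAEs is not required". A separate sentence covers deaths: "Deaths occurring within 4 weeks after the last IMP administration should also be reported", whatever their cause. Section 7.3.2.6 uses the same length for deaths, "even in case the death occurs within 4 weeks after IMP treatment end".

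**On-study reporting.** Section 7.3.4 says: "All SAEs, whether or not they are suspected to be related to study treatment, are to be reported immediately". Section 7.3.2.2 says: "The condition of the patient will be monitored throughout the study".

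**Last contacts.** Flow Chart 9 (Cohort 6) has a Final Visit column with adverse event collection but no day. Section 6.1.11 describes that visit only for the case in which a new inhibitor stops OCTA101, again without a day. Section 4.3.1 names a Termination Visit for withdrawals and gives no timing. Table 2 in Section 6.1.12 has no row for either visit.

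**The concern.** A stopping rule can act only on deaths that reach the sponsor and the DMC. Here the rule and the duty to report use two different lengths, 30 days and 4 weeks. They also use different starting points: study drug in one place, last IMP administration or end of IMP treatment in the others. Once a patient is out of the study, a site could follow Sections 7.3.7 and 7.3.2.6 exactly and still leave a qualifying death unreported or undetected.

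This matters in Cohort 6 because its patients do not finish together. Section 3.2 has three patients starting before the rest, and plans for about 18 to 20 starters so that 16 are evaluable, to allow for early losses. One patient can therefore be out of the study, under local care (Section 4.6), while others inject OCTA101 daily. Those others are the people the rule is meant to protect.

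**Working it through.** No script is needed. The check is day arithmetic and a comparison of sections.

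**1. Length.** Inputs: 30 days (Section 6.2.3.1) and 4 weeks (Sections 7.3.7 a and 7.3.2.6).
- 4 × 7 = 28 days.
- 30 − 28 = 2 days (days 29 and 30) inside the stopping rule and outside the reporting duty.
- 2 / 30 = 6.7% of the window.

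This assumes that both clocks start on the day of the last OCTA101 dose.

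**2. Starting point.** Nuwiq is described in Section 5.1.2, under Investigational Medicinal Products, so it may count as IMP. Suppose study drug means OCTA101 alone, IMP includes Nuwiq, and the last Nuwiq dose comes k days after the last OCTA101 dose. Reporting then runs to day 28 + k after OCTA101, and the gap is max(0, 2 − k):
- k = 0 (patient leaves directly after OCTA101): 2 days
- k = 1: 1 day
- k = 2 or more: 0 days

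If the two terms mean the same products, the gap stays at 2 days whatever k is. The documents do not say which reading is meant.

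**3. Detection on days 1 to 28.** The question is whether a scheduled contact would bring a death to light.
- *Cohort 5:* yes, in part. Samples are due 4 weeks after the 60 IU/kg dose (Section 6.1.6). With the 1-week tolerance in Table 2 this is day 28 ± 7, that is day 21 to day 35.
- *Cohorts 1 and 2, patients with the repeat PK:* seen at day 21 ± 3, that is day 18 to day 24 (Section 6.1.8, Table 2), before either window closes.
- *Cohort 3:* stopped OCTA101 after about 1 month and stayed in the study on Nuwiq until 3 months in total (Section 5.4). The 30 days after OCTA101 were therefore on-study.
- *Cohort 6:* the Final Visit and the Termination Visit exist but have no day and no row in Table 2. Nothing visible ties a contact to day 28 or day 30.

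Cohorts 1 to 3 and 5 are reported as complete, apart from one Cohort 2 patient in immune tolerance induction (Section 3.2). The open gap is therefore in Cohort 6.

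**4. On-study time.** Section 7.3.4 requires immediate reporting of every SAE and Section 7.3.2.2 has patients monitored throughout. Daily dosing runs for months without wash-out between phases (Section 5.4), so most of the time covered by the stopping rule is on-study and has no gap.

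**The case against.** The strongest reply is that this is a small wording mismatch at the edge of the study. Several parts of it stand:
- The 4-week limit applies only after the study, and most time at risk is on-study.
- The length difference is 2 days at most when both clocks start together, and can vanish where Nuwiq follows OCTA101.
- Adverse events are followed until resolved or stable (Section 7.3.2.7), as are those leading to withdrawal (Section 7.3.2.1). A patient who leaves with an open event, the likeliest source of a qualifying death, is therefore followed.
- A minimum duty does not stop an investigator from reporting a day-29 death, and Section 6.2.3.1 separately allows termination on new safety reports.

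A reader might also draw three stronger conclusions that the documents do not support:
- *That deaths are reportable only if the investigator happens to learn of them.* The awareness condition is attached to SAEs; the sentence on deaths has none. The practical difficulty remains, since an unknown death cannot be reported.
- *That no cohort has a contact near the end of either window.* Cohort 5 has one, and Cohort 3 was still on-study.
- *That deaths during the study can escape reporting.* Section 7.3.4 rules this out.

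The reply does not close the gap for a Cohort 6 patient who leaves directly after OCTA101 with no open event. It also rests on discretion for days 29 and 30, where the stopping rule needs a duty.

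**Conclusion.** The point holds for patients who have finished or left the study, and not beyond that. Where the last IMP is OCTA101, days 29 and 30 (2 of 30, 6.7%) meet the stopping-rule window and fall outside the reporting duty. On days 1 to 28 a death is reportable, but post-study SAEs need not be actively sought and no Cohort 6 exit contact is timed, so detection is not assured.

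The documents give no figure from which to calculate a probability; I judge it low. The full consequence needs a qualifying death, after study exit, that goes unnoticed while others are still dosing. A correction is still warranted because a single such death is meant to end a first-in-human study.

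Assumptions: 4 weeks means 28 days; both clocks start at the last OCTA101 dose for the 2-day figure; and the part of Section 7.3.4 missing from the public text adds no post-study follow-up.

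**What to change.** 1. Reconcile the Stopping rules in the Study Outline with Sections 6.2.3.1, 7.3.2.6 and 7.3.7 a) on window length and starting point, so that the reporting period for deaths and SAEs covers whatever period the stopping rule uses. State whether Nuwiq counts as study drug and as IMP for these clocks. The choice of window is for the sponsor and the DMC.
2. For Cohort 6, time the Final or Termination Visit at the end of that period, or add one vital-status and SAE telephone contact there. Enter it in Flow Chart 9 and Table 2, and bring the sentence on proactive monitoring in Section 7.3.7 a) into line.

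Cost: protocol wording and at most one brief contact per patient. No dose or analysis changes.
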